Design:	This is a pilot study conducted at one center, The Ottawa Hospital. It is a Phase 2 open label randomized controlled trial. Consenting participants, meeting all eligibility criteria will be randomized, post PTA procedure, to one of two groups: Rivaroxaban 2.5 mg BID X 90 days plus ASA 81 mg daily OR Clopidogrel 75 mg daily X 90 days plus ASA 81 mg daily Participants will have study drug dispensed at Day 1 and take medication for 90 days. ASA may be continued after the study, for both groups, as per the standard of care. Visits will occur at 7 days, 30 days, 90 days, 6 months and 12 months. Participants will be followed for 12 months (\pm 14 days) in total. Adverse events will be collected for the first 90 days .
Intervention Description:	Treatment Arm 1 Rivaroxaban 2.5 mg twice daily for 90 days (rivaroxaban will be started 6 to 8 hours after the finalization of the procedure) and 325mg of ASA on day 1 then 81 mg of ASA daily for 89 days Treatment Arm 2 Clopidogrel 300mg on Day 1 (loading dose) then 75 mg daily for 89 days and 325mg of ASA on Day 1, then 81 mg of ASA daily for 89 days
Number of participants:	40

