6.3.2 Blood samples

During the entire trial, a volume of approximately 40ml blood will be sampled from each participant for research purposes, in addition to standard of care blood samples: ~10ml of blood (2 x5 ml tubes) will be obtained for research purposes at Day 1, Day 7, and Day 90 for evaluation of platelet activation (including D-dimers), coagulation markers, smooth muscle activation markers (soluble CD40/44 ligands, and ERK ½) and inflammation markers.

All research blood samples will be processed and stored in a freezer at the Thrombosis Group Research Laboratory and analyzed at the conclusion of the study after enrollment has been completed.

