8.1.2 Secondary Outcomes

1. Clinical improvement defined as cumulative improvement of 2 classes of the Rutherford scale without the need for repeated TLR in surviving patients.
2. Event-free survival
3. Overall survival
4. Target lesion revascularization (TLR) between day 1 and final visit
5. Target vessel revascularization (TVR) between day 1 and final visit
6. Peri-procedure death within 30 days
7. Cumulative rate of major adverse cardiovascular events (as defined in 8.1.2.1) between day 1 and final visit
8. Cumulative rate of major bleeding (as defined in 8.1.2.2) between day 1 and day 90.
9. Cumulative rate of minor bleeding (as defined in 8.1.2.2) between day 1 and day 90
10. Biological plausibility by measuring coagulation changes and SMC proliferation markers within 7 and 90 days based on the following markers: D-dimer, soluble CD40/44 ligands, and ERK 1/2.
11. Patency rates based on the ABI index and with an ultrasound at 6 and 12 months
12. Information about feasibility of a future study:
 - a. The total number of eligible candidates identified;

- b. The percentage of eligible patients referred to our study;
- c. The percentage of eligible patients who consent to be enrolled

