8.2 SAMPLE SIZE CALCULATION

Based on recent data published by Conte et al² we expect that during 1 year of follow up, 54% of participants will experience the primary outcome. A total sample of 40 participants was selected and is within the recommended approach for pilot studies evaluating effects when no prior information upon which to base the sample size is available. This sample size will allow us to detect an absolute 20% reduction in the main clinical outcome with a single sided alpha of 0.2 and power of 0.6 as recommended for pilots studies⁵⁹⁻⁶¹. The study will be considered successful if we can demonstrate a reduction in events in the intervention group supported by changes in biomarkers levels (biological plausibility).

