8.3 STATISTICAL ANALYSIS

All the continuous outcomes will be evaluated with the paired T-test or Wilcoxon-rank sum; proportions will be evaluated using the Fisher's exact test.

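### Free improvement: section 8.3 plans no between-arm biomarker comparison that adjusts for the Day 1 value already collected

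*Combined protocol and SAP*

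**What the plan says.** The analysis plan for continuous outcomes is one clause in section 8.3: "All the continuous outcomes will be evaluated with the paired T-test or Wilcoxon-rank sum". It does not say whether the analysis variable is the follow-up value or the change. It names no time point, covariate or model, and no baseline-adjusted analysis appears elsewhere in the document.

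The biomarkers are the continuous outcomes that matter most here:

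- Section 8.1.2, item 10, lists "Biological plausibility by measuring coagulation changes and SMC proliferation markers within 7 and 90 days" and names D-dimer, soluble CD40/44 ligands and ERK 1/2.
- Section 6.3.2 says that the research blood "will be obtained for research purposes at Day 1, Day 7, and Day 90". Appendix 1 shows the same three draws.
- Section 8.2 calls the study successful if events fall in the intervention group, "supported by changes in biomarkers levels (biological plausibility".

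On size, section 8.2 states "A total sample of 40 participants was selected". The synopsis says that participants "will be randomized, post PTA procedure, to one of two groups", without an allocation ratio.

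**The concern.** Part of the success rule rests on markers compared in about 20 patients per arm. At that size the comparison is limited by between-patient spread, and a chance imbalance at Day 1 is quite possible. A Day 1 measurement that correlates with the later values can reduce both problems without any extra sample.

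Neither named test makes full use of it. The paired t-test uses Day 1, but only to ask whether patients changed; it does not compare two independent arms. The rank-sum compares arms but takes no covariate. Run on Day 7 or Day 90 values, it ignores Day 1. Run on change from Day 1, it carries the Day 1 noise in full. What is at stake is avoidable imprecision in the biomarker half of the success rule.

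**Working it through.** **The plan's own figure.** There is none for the biomarkers. The design statement "with a single sided alpha of 0.2 and power of 0.6" belongs to the primary binary outcome, for which section 8.2 expects that "54% of participants will experience the primary outcome". I borrow its alpha only as a reference level.

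**Inputs**
- From the documents: 40 participants (8.2) and draws at Days 1, 7 and 90 (6.3.2).
- Assumed: 1:1 allocation, so n = 20 per arm; a true between-arm difference of 0.5 SD; equal SD at Day 1 and follow-up on the analysis scale; one-sided alpha 0.2; correlation r between Day 1 and follow-up of 0.3, 0.5 and 0.7, with r = 0 as the worst case.

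**Step 1: variance factor v, relative to comparing follow-up values**
- Follow-up value only: v = 1.
- Change from Day 1: v = 2(1 − r), giving 1.40, 1.00, 0.60.
- Adjusted for Day 1: v = 1 − r², giving 0.91, 0.75, 0.51.

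For 0 < r < 1, 1 − r² is below 1. It is also below 2(1 − r), because 1 − r² = (1 − r)(1 + r) and 1 + r < 2. Adjustment is therefore more precise on either reading of 8.3.

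**Step 2: charge adjustment for its small-sample cost.** The model loses one degree of freedom (38 to 37). Chance Day 1 imbalance inflates the expected variance by (40 − 3)/(40 − 4) = 37/36. The adjusted factors become:
- r = 0.3: 0.91 × 37/36 = 0.935
- r = 0.5: 0.75 × 37/36 = 0.771
- r = 0.7: 0.51 × 37/36 = 0.524
- r = 0: 1 × 37/36 = 1.028

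After this charge, adjustment still beats follow-up values when r² > 1/37 (r above about 0.16). It beats change scores when 1 + r < 72/37 (r below about 0.95).

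**Step 3: power.** Noncentrality is 0.5 / √(2v/20), referred to a noncentral t. For example, v = 1 gives 0.5/0.316 = 1.581 and power 0.768. Adjusted at r = 0.5, it is 0.5/√0.0771 = 1.801 and power 0.829.

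| r | Follow-up only | Change | Adjusted, cost charged | Gain over better simple analysis |
|---|---|---|---|---|
| 0.3 | 0.768 | 0.687 | 0.784 | 0.016 |
| 0.5 | 0.768 | 0.768 | 0.829 | 0.061 |
| 0.7 | 0.768 | 0.883 | 0.909 | 0.026 |
| 0 | 0.768 | 0.607 | 0.761 | −0.007 |

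**Step 4: sensitivity to alpha.** At one-sided 0.025, follow-up values give 0.338 and change gives 0.255, 0.338, 0.512. Adjustment with its cost charged gives 0.357, 0.418, 0.566. The gains are about 2, 8 and 5 points.

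**Step 5: check with the rank-sum itself.** Steps 3 and 4 use a t-test, so a simulation of 3,000 runs per setting was made with normal data, 20 per arm, a 0.8 SD effect and two-sided 5%. At r = 0.3, 0.5, 0.7:
- Rank-sum on follow-up: 0.67, 0.68, 0.67.
- Rank-sum on change: 0.54, 0.68, 0.88.
- Adjusted model: 0.74, 0.81, 0.93.

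The direction is the same.

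**The case against.** **Day 1 may already be used between arms.** A reader might infer from 8.3 that the Day 1 value plays no part in any between-arm comparison. The documents do not support that. Sections 8.1.2 and 8.2 both speak of changes, and 8.3 does not exclude a rank-sum on change from Day 1. This stands. What survives is that neither form of the rank-sum adjusts for Day 1, and both are less precise than a model that does.

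**The gain is small and rests on assumptions.** One could quote the rise from 0.77 to 0.91 at r = 0.7, but that compares adjustment only with discarding Day 1. Against the better simple analysis the gain is 2 to 6 points. The correlation, effect size and allocation are not in the documents, and no alpha is set for the biomarkers. This also stands.

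**Day 1 may not be a true baseline.** Section 6.2.1 lists the blood draw among the Day 1 data without placing it relative to the ASA loading dose, heparin, the procedure, randomization or the first study dose; 6.3.2 adds nothing. If it follows the first randomized dose, adjusting for it could remove part of the treatment effect. If it is taken before that dose but around the procedure, r could be low. This stands as a condition on the fix.

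**ABI.** A reader might extend the point to ABI because a screening value is recorded. That does not follow. Section 8.1.2, item 11, uses ABI for patency rates, which are proportions. Section 8.1.1.3 measures an ABI drop from the post-procedure value, whereas the screening ABI predates the procedure.

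**Larger gaps exist.** The biomarker criterion has no threshold or time point, and a paired test is not a between-arm test. Both are true and more serious, but they do not make the missing adjustment right.

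**Conclusion.** The point holds as a nearly free gain in precision. It does not show that the planned rank-sum is invalid. Section 8.3 specifies no between-arm biomarker analysis adjusted for Day 1, although the sample is drawn and biomarker change enters the success rule.

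With 20 per arm, a 0.5 SD effect, one-sided 0.2 and r from 0.3 to 0.7, adjustment adds about 2 to 6 points of power over the better simple analysis. If r is 0 it costs less than 1 point. The direction is secure for any moderate positive correlation; the size depends on an r that the documents do not give. All of it is conditional on the Day 1 sample preceding the first randomized dose. The point is confined to the biomarkers.

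**What to change.** In section 8.3:

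- For each marker, log-transformed, compare arms at Day 7 and at Day 90 with a linear model containing treatment and the log Day 1 value.
- Report the adjusted between-arm ratio with its confidence interval.
- Keep the rank-sum as a sensitivity analysis, and say whether it is run on follow-up values or on change.
- State that Day 1 is used as the covariate only if the sample was drawn before the first dose of randomized study drug. Record the draw time in sections 6.2.1 and 6.3.2.

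No ABI model is needed for this point. The cost is a few sentences and a few lines of code, with no new patients, visits or samples. Section 6.3.2 holds the samples for analysis after enrollment is complete, so the text can be settled before any marker result exists.

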9 STUDY ADMINISTRATION

9.1 APPLICABLE STANDARDS AND REGULATIONS

The trial will be performed in compliance with the Canadian Tri-Council Policy Statement version 2 (TCPS2), the World Medical Association Declaration of Helsinki, adopted by the 18th World Medical Assembly, Helsinki, Finland, June 1964, and last amended by the 52nd WMA General Assembly, Edinburgh, Scotland, October 2000, the Canadian Food and Drug Regulations, Division 5 Part C, the Canadian Ontario's Personal Health Information. Protection Act (PHIPA), and the ICH Good Clinical Practices (GCP).

9.2 ETHICAL CONDUCT OF THE STUDY

9.2.1 Ethics Committee

The trial may only be initiated after the Investigator has obtained written approval of the protocol, Informed Consent form and other study documents, and any amendments (if applicable), by the Ottawa Health Science Network Research Ethics Board (OHSNREB). Changes in protocol (amendments) must be submitted to the OHSNREB for approval. Reports on, and reviews of, the trial, its safety aspects and its progress will be submitted to the OHSNREB by the Investigator at intervals according to the institutional guidelines.

9.2.2 Identification of potential participants

Enrollment will be conducted at the Vascular Surgery Outpatient Clinic and on the wards at the Ottawa Hospital Civic Campus. To increase our screening for eligible participants, all scheduled PTAs will be screened daily for eligibility and a screening log will be maintained.

9.2.3 Participant Information and Consent

All relevant study information will be summarized in an informed consent form. The investigator or delegate will explain all relevant aspects of the study to the patients prior to entry into the study (i.e. before any examinations and procedures associated with the selection for the study are performed or any study-specific data is recorded on study-specific forms). The patient will have ample time and opportunity to ask questions and will be informed about the right to withdraw from the study at any time without any disadvantage and without having to provide reasons for their decision.

9.3 STEERING COMMITTEE

A Steering Committee comprised of the trial's co-investigators will manage the overall conduct of the trial. Drs. [name], [name] and [name] will regularly review the progress of the trial. The Steering Committee will review how the trial was conducted and review the various outcomes of the trial to determine if the evidence justifies a full randomized trial.

9.4 DATA MANAGEMENT

Data will be recorded on a paper case report form (CRF) by the research personnel according to the protocol. CRFs will be verified for completeness and accuracy by a research team member not involved in the data collection. Any changes to the CRF will be tracked. Upon completion of data collection and verification of the CRF by the Investigator or designee, data will be entered in an data analysis software. Data will be cleaned and coded prior to analysis by a statistician. Missing data will be queried. Data still missing after queries will be coded appropriately by the statistician. Reports will be prepared prior to Data Safety Monitoring Board (DSMB) meetings including: enrollment per treatment arm, descriptive statistics for demographic data (and other relevant characteristic) to assess that randomization was effective, and a tabulated summary of AEs and SAEs per treatment arm.

9.5 DATA QUALITY

9.5.1 Role of the Data Safety Monitoring Board

This study will be monitored by an independent Data Safety Monitoring Board (DSMB), consisting of an independent physician, and two other members not involved in this study. The DSMB will be immediately informed of any serious adverse events (SAEs), which are potentially related to study drug. If at any point the DSMB considers continuance of the study unacceptable, the steering committee will be immediately notified.

The DSMB will have a scheduled meeting midway through the trial (after ~20 participants have completed the first 90 days of the trial or after 6-months of active recruitment). An interim report will be prepared by the data management team for the study. The report will include data on recruitment, compliance, adverse events, baseline comparability and treatment comparisons.

If at any point the DSMB considers continuance of the study unacceptable, the steering committee will be immediately notified.

9.5.2 Monitoring

The investigator (or his/her delegate) agrees to cooperate with the OHRI monitor to schedule at least one monitoring visit during the course of the study and to ensure that any problems detected in the course of this monitoring visit are resolved. This monitoring by OHRI does not replace the routine quality control to be performed by the Qualified Investigator or his delegate.

Routine quality control will be completed by the Qualified Investigator or his delegate to ensure that the study is being run according to the protocol. The routine monitoring of the study will include:

- Verification of all inclusion and exclusion criteria to confirm that only eligible participants are participating in the trial
- Verification of source data to ensure accuracy of study data as per the monitoring plan
- Verification that adverse events are recorded, assessed and reported according to the protocol
- Verification of the case report forms to ensure that they are being completed according to the protocol

9.5.3 Audits

The Investigator should understand that OHRI or its delegates, after appropriate notification may audit the study for Quality Assurance purposes.

9.5.4 Adjudication of outcomes

The primary outcome, bleeding events and major adverse cardiovascular events will be adjudicated by a blinded expert adjudication committee.

10 RECORD RETENTION

To comply with Health Canada regulations, the trial related records will be retained for 25 years. Records will be kept to enable linkage of participants' identity to CRF data (master log). This includes sufficient information from hospital and clinic records such as all original signed informed consent forms, source records, and detailed records of cell manufacturing. After 25 years, all study records will be destroyed by shredding or incineration

11 ANTICIPATED RESULTS- DISSEMINATION PLAN

The results of our trial will be used by the investigators to evaluate the need for further studies evaluating the role of the addition of rivaroxaban to reduce clinically relevant outcomes in patients with CLI requiring PTA and will provide justification to external funding agencies before a commitment is made to fund a full trial.

Regardless of the results of the trial, we will make every effort to publish and present our data and conclusions about feasibility such that future researchers might benefit from this work.

The International Committee of Medical Journal Editors (ICMJE) member journals have adopted a trials-registration policy as a condition for publication. This policy requires that all clinical trials be registered in a public trials registry such as ClinicalTrials.gov*, which is sponsored by the National Library of Medicine. It is the responsibility of the QI to register this trial in an acceptable registry on or before patient enrollment.

12 CONFIDENTIALITY

All subject related information including Case Report Forms, evaluation forms, reports, etc. will be kept strictly confidential. All records will be kept in a secure, locked location and only research staff will have access to the records. Subjects will be identified only by means of a coded number specific to each subject. All computerized databases will identify subjects by numeric codes only, and will be password protected or encrypted.

Upon request, subject records will be made available to the study sponsor, monitoring groups' representative of the study sponsor, and applicable regulatory agencies such as Health Canada.

APPENDIX 1: SCHEDULE OF EVENTS

	Screening Visit -30 days to -1 day	PTA Baseline Day 1	Visit Day 7 (+/- 3 days)	Visit Day 30 * (+/- 14 days)	Visit Day 90 (- 14 days)	Visit 6 months* (+/-30 days)	Final Visit 12 months* (+/-30 days)
Informed Consent	X						
Inclusion & Exclusion Criteria	X						
Physical Exam ¹	X						
Medical History	X						
Randomization		X					
Dispense study medication		X					
Study medication compliance review			X	X	X		
Rutherford Score	X	X		X		X	X
Review of bleeding events	X	X		X	X	X	X
Review of major cardiac events		X		X	X	X	X
Review of Re-interventions				X	X	X	X
Review of Adverse Events		X	X	X	X	X	X
Clinical Laboratory Tests Results ²	X						
Review of Concomitant Medications	X	X		X	X	X	X
Collect Imaging Outcomes				X		X	X
Blood Work, research samples ³		X	X		X		

¹ Height and weight

² CBC, coagulation tests, and serum creatinine

³ Includes: Platelet activation, coagulation markers, smooth muscle activation, inflammation markers

*Visit may be completed in person or via telephone follow-up

6. SAE status/clinical outcome

- Recovered/Resolved
- Not yet recovered
- Recovered with sequelae
- Fatal/Death
- Unknown

Date & Time:

Date (dd/mmm/yyyy): / /

Time: : (24 hour clock)

7. Event Description

Include a history of the event chronologically including signs and characteristics, severity, dates and outcomes of hospitalization and any other relevant information not captured elsewhere on the form. Include relevant tests/data, treatment/procedures, medical history, treatment history.

8. Relevant tests/data source documents have been attached?

No

Yes

9. Relevant treatment/procedures source documents have been attached?

No

Yes

10. Relevant medical history source documents have been attached?

No

Yes

11. Relevant previous treatment history (including operations or medical procedures) source documents have been attached?

Yes No

12. Study Medication # 1

Study Medication Name: Aspirin

Dose: 81 mg Frequency: once daily

Route: oral

Lot number:

Expiry date (dd/mmm/yyyy): / /

Indication for use: anti-platelet

Date of first dose: (dd/mmm/yyyy): / /

Time of first dose: : (24 hour clock)

Date of last dose prior to SAE: (dd/mmm/yyyy): / /

Time of last dose prior to SAE: : (24 hour clock)

13. Action taken with study drug #1 (Aspirin)

- Temporarily discontinued
- Permanently discontinued
- Nil
- Other:

14. Is there a reasonable possibility that the SAE is related to study drug #1?

- Yes No Not assessable

15. If study drug #1 is temporarily interrupted:

Stopped on (dd/mmm/yyyy): / /

Restarted on (dd/mmm/yyyy): / /

Event abated after study drug #1 stopped? Yes No N/A

Did event reappear after reintroducing study drug #1? Yes No N/A

16. Study Medication # 2

Study Medication Name: _____

Dose: _____ Frequency: _____

Route: oral

Lot number:

Expiry date (dd/mmm/yyyy): / /

Indication for use: _____

Date of first dose: (dd/mmm/yyyy): / /

Time of first dose: : (24 hour clock)

Date of last dose prior to SAE: (dd/mmm/yyyy): / /

Time of last dose prior to SAE: : (24 hour clock)

17. Action taken with study drug #2

- Temporarily discontinued
- Permanently discontinued
- Nil
- Other:

18. Is there a reasonable possibility that the SAE is related to study drug #2?

Yes No Not assessable

19. If study drug #2 is temporarily interrupted:

Stopped on (dd/mmm/yyyy): / /

Restarted on (dd/mmm/yyyy): / /

Event abated after study drug #1 stopped? Yes No N/A

Did event reappear after reintroducing study drug #1? Yes No N/A

20. Concomitant Medications (exclude those used to treat reaction) source documents have been attached? Yes No

21. Intensity

Mild Moderate Severe

To be completed by investigator only !

22. Causality:

Unrelated Possibly related Related

To be completed by investigator only !

23. Expectedness

Expected Unexpected More prevalent

To be completed by investigator only !

24. Possible causes of the event (check all that apply): To be completed by investigator only !

- Pre-existing/Underlying disease: _____
- Study treatment: _____
- Other treatment (concomitant or previous): _____
- Protocol-related procedure: _____
- Other (e.g. accident, new or intercurrent illness) : _____

Research Staff's Name: _____

Research Staff Signature: _____

Investigator's Name: _____

Investigator's Signature: _____

Date (dd/mmm/yyyy): / /

